**REGULATORY FRAMEWORK:**

Please indicate all that apply:

	DOD (Department of Defense)
	DOE (Department of Energy)
	DOJ (Department of Justice)
	ED (Department of Education)
	EPA (Environmental Protection Agency)
	FDA (Food and Drug Administration)
	HHS (Department of Health and Human Services)
	VA
	Other:

Is this a clinical trial under ICH-GCP E6?  Yes  No

If yes, please confirm that the research team is familiar with and agrees to comply  
 Yes  No

with the investigator requirements cited in ICH-GCP E6.

ICH-GCP E6 can be accessed by copying and pasting this URL into your browser: <http://www.fda.gov/downloads/Drugs/Guidances/ucm073122.pdf>

FUNDING: P20 GM109089 06 – Sub#6857

## 1. Objectives

### 1.1. Describe the purpose, specific aims, or objectives.

The *purpose* of the proposed research is to develop a novel, precise, and individualized approach to modulate motivational neurocircuits in order to ameliorate apathy in traumatic brain injury (TBI). Recent work by the PI and collaborators suggests that damage to ventromedial prefrontal cortex (vmPFC) or dorsal anterior cingulate cortex (dACC) can cause elevated apathy in patients with TBI. Additionally, the PI and collaborators at the Center for Brain Recovery and Repair (CBRR) recently found that heightened connectivity between these structures may provide a compensatory response, reducing apathy in the wake of a TBI. We are currently conducting a related study using task-evoked fMRI to determine the specific neural computations that may be encoded in vmPFC-dACC circuits during motivated decision making in patients with TBI (#19-053), and the present protocol represents a separate but related line of research designed to use precise fMRI-guided transcranial magnetic stimulation (TMS) to stimulate vmPFC-dACC circuits and modulate motivated behavior in healthy controls (HCs). The *purpose* for this project is clear: fMRI-guided TMS could represent a viable approach for treating apathy in TBI, but achieving this goal requires a better understanding of the effectiveness of fMRI-guided TMS approaches for engaging those circuits. We will achieve our overall objective through the following *specific aims*:

- i) To measure individualized patterns of vmPFC and dACC activation and connectivity during task-evoked fMRI.
- ii) To use these activation patterns to guide brain stimulation using TMS.
- iii) To measure TMS-induced changes in brain activation and connectivity using fMRI.

### 1.2. State the hypotheses to be tested.

- i) dACC TMS will modulate motivated decision making.
- ii) dACC TMS will increase post-TMS recruitment of the brain networks underlying motivated behavior.

## 2. Background

### 2.1. Describe the relevant prior experience and gaps in current knowledge.

TBI is a common and impairing acquired neurological disorder caused by a concussive event to the head. Psychiatric disorders associated with impaired decision making—namely, compulsivity, depression, and impulsivity—are common symptoms post-injury in TBI. Despite the critical importance of diagnosing and characterizing psychiatric problems in TBI, very little is known about the neuropathologies underlying psychiatric symptoms in this patient group.

## NONINVASIVELY MODULATING MOTIVATIONAL BRAIN REGIONS

Reinforcement learning (RL)—i.e. the process of learning the reward value of stimuli and actions—represents a fundamental cross-species construct underlying motivated decision making. Further, aberrant RL and reward processing more broadly have been strongly implicated in symptoms of compulsion, depression, and impulsivity in the field of computational psychiatry. Despite extensive evidence that brain injuries can lead to maladaptive motivated decision making, the specific RL aberrations that might underlie this phenomenon, and their association with psychiatric sequelae remain unclear. Therefore, extant work has failed to provide insight into the computational mechanisms underlying maladaptive decision making in patients with TBI, and such work will be critical to build a better understanding of the neuropathologies that underlie psychiatric sequelae in TBI. This gap in current knowledge is being targeted by our related protocol #19-053.

However, even if we have a better understanding of the RL neural mechanisms that cause aberrant motivated behavior and psychiatric sequelae in TBI, how to translate this into an actionable target for clinical intervention remains unclear. Psychological interventions including Cognitive-Behavioral Therapy (CBT) and Motivational Interviewing (MI) have been investigated for treating symptoms of TBI. Early trials suggest that CBT fails to show a beneficial effect on its own, but when delivered alongside MI—an approach designed to reduce patient apathy—a modest reduction is observed. However, the potential benefit of both CBT and MI is limited in TBI, as they both rely heavily on high-level cognitive abilities—e.g. selective attention, executive control, and metacognition/insight—that are commonly impaired in this clinical population. In addition to psychotherapies, two categories of pharmacotherapy have been investigated to reduce psychiatric sequelae in TBI: selective serotonin reuptake inhibitors (SSRIs) and dopamine agonists. A randomized controlled trial of SSRIs for TBI failed to demonstrate reductions in patient neuropsychiatric symptoms after a 10-week intervention. Multiple pilot studies (Ns=10-11) of dopamine agonists for TBI have been conducted, demonstrating preliminary support that they may reduce apathy. Yet, a recent meta-analysis suggested a high degree of unreliability in the literature on dopamine agonism in TBI. Dopamine agonists also carry the risk of significant side effects including *increased apathy* or maladaptive impulsivity. Unreliability and maladaptive side effects of dopaminergic medications are likely driven by their lack of circuit-specificity: They modulate dopaminergic tone throughout the brain, rather than within a dedicated neural circuit underlying a specific symptom profile. *Therefore, a more effective approach to treating apathy in TBI may involve both i) avoiding therapies that rely on high-level cognition, and ii) establishing circuit-specific approaches for ameliorating patient apathy.* Precise fMRI-guided TMS represents one possible approach. The current project aims to test the efficacy of fMRI-guided TMS to RL neural circuits anchored in dACC on motivated decision making in HCs. Ultimately, the hope is that this approach might represent a first step towards a potential clinical intervention for TBI patients with clinical apathy.

*2.2. Describe any relevant preliminary data.*

The PI has previously published on how damage to ventromedial prefrontal cortex (vmPFC) can cause significant apathy in patients with traumatic brain injury. Additionally, the study team recently leveraged extant data available in the center to demonstrate that *enhanced* connectivity between vmPFC and dorsal anterior cingulate cortex (dACC) represents a potential compensatory mechanism for reducing apathy in the wake of a mild TBI injury. This dACC target, and enhanced dACC-vmPFC connectivity, will represent the critical targets for TMS neuromodulation in the current study.

*2.3. Provide the scientific or scholarly background for, rationale for, and significance of the research based on the existing literature and how will it add to existing knowledge.*

Dopamine agonists have demonstrated limited efficacy for ameliorating apathy in TBI, but they have significant side effects because they are circuit-general (e.g. modulate dopaminergic tone across the brain). Conventional repetitive TMS (rTMS) can induce circuit-specific changes, but its rate limiting factor is the method used to determine the target region of interest (ROI). In contrast, task fMRI-guided rTMS has the potential to enable localization of a circuit relevant to a specific symptom, and selective enhancement of excitability in that circuit. The *rationale* for this approach is that, while fMRI-guided rTMS is an established method for making causal brain-behavior inferences, its therapeutic potential for circuit-specific neuromodulation has not been fully realized.

### **3. Study Design**

*3.1. Describe the study design (e.g., observational; randomized placebo-controlled clinical trial, etc.)*

This is a brain stimulation / HC arm of an existing protocol (#19-053). The current protocol describes a clinical trial where we will focus on the causal effect on decision-making of rTMS targeting dACC using a fully randomized, within-subjects, sham- controlled experimental design.

### **4. Inclusion and Exclusion Criteria**

*4.1. Describe how individuals will be screened for eligibility.*

- Participants will be phone-screened to determine their eligibility, and the phone screen and script are provided in **Appendices 1–2**.

*4.2. Describe the criteria that define who will be included or excluded in your final study sample.*

## NONINVASIVELY MODULATING MOTIVATIONAL BRAIN REGIONS

- The protocol will recruit male and female adults (18-55 years old) of any ethnic background. All recruited participants will be capable of providing informed consent.
- Participants will have 12 or more years of education and the ability to provide informed consent independently.
- Exclusion criteria will be: any condition that would prevent the subject from being able to complete the protocol, prior history of neurological disease or any history of seizures (including prior history of TBI; i.e., any loss of consciousness  $\geq 1$  minute), not fluent in English, any contraindications to MRI or TMS (**Appendices 3-4**), history of substance abuse (excluding moderate alcohol or marijuana usage), a medical diagnosis of psychosis or mania, or stable doses of antipsychotics or mood stabilizers taken for less than two months.
- Participants who are found to have falsely represented any factors which should exclude them from the study, or who are unable to follow the study protocols for study session attendance may be withdrawn prematurely from the study.
- To reduce the possible spread of COVID-19, during the SARS-CoV-2 pandemic any participants who answer “yes” to any of the items in Question 34 of the Phone Screen (**Appendix 1**) will be excluded from the study at this time.

*4.3. Indicate specifically whether you will include each of the following special populations: (You may not include members of the above populations as subjects in your research unless you indicate this in your inclusion criteria.)*

The study will not recruit from the following special populations: adults unable to consent, individuals who are not yet adults, pregnant women, or prisoners.

*4.4. Indicate if you excluding any particular populations (e.g., women, children, persons not fluent in English, a particular racial or ethnic group, etc.) and provide justification.*

Individuals not fluent in English will have difficulty performing the behavioral assays used in the current protocol, and will find it difficult to understand the study protocols to the point where they are capable of providing truly informed consent. Accordingly, proficiency in the English language is a requirement for the current protocol.

## 5. Number of Subjects

*5.1. If this is a multicenter study, indicate the total number of subjects to be accrued across all sites.*

N/A – This is a local single-site protocol.

*5.2. Indicate the number of subjects to be recruited at this site.*

42 HC participants will be recruited.

### *5.3. Provide sample size justification*

Prior studies using fMRI-guided TMS to modulate task-related neural computations have observed effect sizes of approximately  $d \approx 1.02^{67-69}$ , requiring a sample of  $N=17$  per stimulus condition. Therefore, even if a high attrition rate of 20% is factored into the current study protocol, the protocol will achieve an adequate sample size to detect true differences as a function of stimulation condition.

## **6. Study Timelines**

### *6.1. Describe:*

Participants recruited for the study will be invited to complete three experimental sessions as soon as it is convenient for them to come in. The three experimental sessions will include one MRI scan (1-2 hours per scan). The first session will include all questionnaires and assessments (maximum time: 170 minutes, see Table 1). The second and third sessions will include rTMS administration including motor thresholding ( $\approx 20-40$  minutes), neuronavigation ( $\approx 10-20$  minutes) and rTMS delivery ( $\approx 3-20$  minutes, depending on the specific pulse sequence). The total rTMS session will last  $\approx 1-1.5$  hours, and will be immediately followed by an MRI scan (total session time: 3-4 hours for day 1, 4-5 hours for day 2). It is expected that data collection targets will be reached by September, 2022.

## **7. Study Endpoints**

### *7.1. Describe the primary and secondary study endpoints.*

The study will end when  $N=42$  HC have completed the protocol.

### *7.2. Describe any primary or secondary safety endpoints.*

N/A – The study is minimal risk and no safety endpoints are necessary.

### *7.3. Describe any exploratory endpoints.*

N/A – The study design does not include any exploratory endpoints.

## **8. Research Setting**

### *8.1. Describe the sites or locations where your research team will conduct the research.*

The study will be conducted in Domenici Hall on the UNM North Campus, at the Mind Research Network (MRN) also located in Domenici Hall, and in the Department of Psychology at Logan Hall on the main campus.

### *8.2. Identify where your research team will identify and recruit potential subjects.*

All participants will be recruited from the community and from study 19-053: Reward-guided decision making in patients with moderate-to-severe traumatic brain injury (msTBI), who were contacted via the following strategies:

## NONINVASIVELY MODULATING MOTIVATIONAL BRAIN REGIONS

- i) Participants who have participated in previous studies at the CBRR and consented to be contacted for future research opportunities.
- ii) Fliers posted in the community and online (**Appendices 5-7**), and word of mouth.

*8.3. Identify where research procedures will be performed including any laboratory analytics*

Analytic procedures will be conducted at the MRN, CBRR, and Logan Hall.

*8.4. Describe the composition and involvement of any community advisory board*

N/A – There is no community advisory board.

*8.5. For research conducted outside of UNM HSC and its affiliates describe:*

There will be no research conducted outside UNM / HSC / MRN.

## 9. Resources Available

*9.1. Describe the qualifications of the PI and study staff (e.g., training, experience, oversight) as required to perform the research. When applicable describe their knowledge of the local study sites, culture, and society.*

The PI has extensive experience studying affective and reward processes in HC and patients with TBI. The PI also has experience with fMRI: The PI has experience running the MRI scanner and preparing a diverse range of subjects to be scanned, been first author on two peer-reviewed manuscripts using fMRI, and has completed both a week-long fMRI course at the Harvard-MIT Martinos Center for Biomedical Imaging, and a three-day fMRI course at the MRN. The PI has also published several papers using TMS, containing a total of 95 safely-completed TMS sessions, and recently completed an extensive hands-on refresher course on the safe and efficient administration of TMS protocols in [name]'s world-class brain stimulation laboratory in the Department of Psychiatry at the Medical University of South Carolina (**Appendix 8**). Therefore, the PI is well qualified to lead the current research protocol.

All study personnel will have been trained and certified in safe MRI practices at MRN, and will have received required training sessions in order to gain access to the UNM Noninvasive Neurostimulation Lab (PI: [name]).

[name] oversees all projects being conducted at the Clinical Neuropsychology Research Core within the CBRR, and is well qualified to advise the PI while the current project is being carried out. Finally, the entire study team (including all research assistants) have completed the required CITI training modules, and have experience collecting behavioral and neuroimaging data from human participants.

## NONINVASIVELY MODULATING MOTIVATIONAL BRAIN REGIONS

### *9.2. When applicable, describe which licensed physicians/providers will be responsible for medical decision-making and ordering and evaluation of necessary diagnostics and therapeutics.*

Within 24 hours, the Beck Depression Inventory (BDI) will be examined for endorsement of suicidal ideation. If the participant endorses suicidal ideation (scoring 2 or 3 on item #9 of the BDI) the PI will be immediately notified. The participant will then be contacted over the phone by a senior member of the research team. This protocol will be done in consultation with attending psychiatrists at the UNM Psychiatric Center.

This phone screen protocol consists of multiple steps to protect participant confidentiality:

- 1) The experimenter will verify via person-to-person contact with the participant that this is a “*good time to talk discreetly*” prior to raising the reason for the call about the depression rating score for suicidality.
- 2) If the participant endorses thoughts of suicidality they will be notified of number of local counseling and psychiatric resources, including 24-hour hotlines and free or low-cost counseling services.
- 3) If the participant endorses imminent suicidal ideation, the PI will call 911 to inform emergency responders of the participant’s location and imminent suicide plans.

Additionally, all research MRI scans at MRN will be read for incidental findings by a radiologist.

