## NONINVASIVELY MODULATING MOTIVATIONAL BRAIN REGIONS

11	Toronto Alexithymia Scale	5
12	The Next Big Five Inventory	5
13	Beck Anxiety Inventory	5
14	Beck Depression Inventory	5
15	Posttraumatic Stress Disorder checklist	5
16	Substance & Alcohol Use Questionnaires	10
17	Practice of fMRI Task ('Bandit Task')	5
18	Practice of fMRI Task #2 ('Apples Task')	5
ALL	Total	170 minutes

- **Demographics:** The Demographics spreadsheet includes background information on ethnicity, education, alcohol, and medications. It is attached in **Appendix 10**.
- **Rivermead Post Head Injury Questionnaire:** Is a semi-structured, gold standard interview used to assess each participants' TBI history in depth. This is primarily to provide evidence that HC participants in this study have quantifiably fewer / less severe TBI histories than patients in Study #19-053. It is attached in **Appendix 11**.
- **Apathy Evaluation Scale (AES):** Is an 18-item self-report measure used to assess apathy symptoms in individuals with neurological disorders such as TBI. It is attached in **Appendix 12**.
- **Apathy Motivation Index (AMI):** Is an 18-item self-report measure used to assess apathy symptoms in individuals with neurological disorders similar to the AES, but also assays a dimension known as “social-motivational apathy”. It is attached in **Appendix 13**.
- **Neurobehavioral Symptom Inventory (NSI):** The NSI is a 22-item self-report questionnaire designed to probe the specific set of sequelae experienced by patients with TBI. Patients rate the degree to which they have experienced a set of common symptoms on a scale of 0-4, depending on how severely they have disturbed the patient in the past two weeks. It is attached in **Appendix 14**.
- **NIH-Toolbox Cognition Battery (NIH-TB):** The NIH-TB is a comprehensive set of standardized cognitive assessments developed by the NIH to evaluate a range of cognitive functions—including attention, episodic memory, executive function, language, processing speed, and working

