- **Alcohol Use Disorder Identification Test (AUDIT):** the AUDIT is a gold standard self-report assay dealing more specifically with the consumption of alcohol and is attached in **Appendix 24**.
- **Bandit Task:** The Bandit task is the gold standard for isolating the neural circuits underlying explore/exploit decision making in humans and nonhuman primates. During this task, participants select between images with varying probabilities of receiving a reward. After learning the reward values of each picture over a series of trials, at random intervals one of the pictures is swapped for a novel picture with a randomly assigned reward value that may be higher or lower than the remaining familiar pictures. This process is repeated for a series of trials, and participants are told that if they score high enough on a randomly selected trial, they will earn a bonus \$20. In actuality, the \$20 will be awarded to all participants as part of the standard compensation rate at the end of the experiment. Therefore, this process will motivate participants to accumulate points on the task, but will be evenly compensated no matter how they do on the task. A random set of pictures will be randomly selected from the International Affective Picture System (IAPS) for each participant. The task was programmed by the PI, and a sample trial image is provided in **Appendix 25**. A brief practice version of the Bandit task will be performed with a research team member prior to the MRI portion on day 1, 2 or 3 of the protocol ( $\approx$ 3 minutes).

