- **Apples Task:** The Apples task is an effort-based decision-making task that will be performed during MRI data collection on all days of the protocol. Participants will begin by practicing effortful grips requiring a certain percentage of their maximum voluntary contraction on a dynamometer (%MVC; **Appendix 26**). After experiencing the effort required to execute various %MVC grips, participants will be asked to make a series of reward-effort tradeoff decisions (**Appendix 26**). Each trial will randomly sample the parameter space between 20 and 100%MVC and one to thirteen apples. Participants will be told that at the end of the session the experimenter will select a random set of 10 responses they said ‘yes’ to during the MRI, but in reality (similar to the Bandit task) all subjects will receive a \$20 bonus for completing the task. This will ensure participants are motivated, without placing a burden on them in terms of their physical effort requirement. A brief practice version of the task will be performed with a research team member prior to the MRI portion on day 1 of the protocol ( $\approx$ 5 minutes).
- **TMS Protocol:** On day 2 and 3 of the protocol, single pulses of TMS will be applied over the scalp area overlying the participants’ motor cortex using a

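### Section 9.2 lets BDI item 9 go unread for up to 24 hours, so a participant scoring 2 or 3 can leave session 1 before anyone has seen the answer

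*Combined protocol and SAP*

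**What the plan says.** Section 9.2 sets the review deadline: "Within 24 hours, the Beck Depression Inventory (BDI) will be examined for endorsement of suicidal ideation". It does not say when the 24 hours begin. The trigger is a score of 2 or 3 on item 9. Once that score is seen, "the PI will be immediately notified", and next: "The participant will then be contacted over the phone by a senior member of the research team". Attending psychiatrists are consulted, local resources and hotlines are offered, and the PI calls 911 if ideation is imminent.

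The timing of the BDI comes from elsewhere in the protocol:

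- Section 6.1: "The first session will include all questionnaires and assessments", with a maximum of 170 minutes. Each session has a scan of 1–2 hours, and the day-1 total is given as 3–4 hours.
- Section 12, Table 1: "Beck Depression Inventory" is 14th of 18 items.
- Section 12, Apples Task: the practice, which is the last item in Table 1, is "performed with a research team member prior to the MRI portion on day 1 of the protocol".
- Section 12, Bandit Task: its practice may fall "prior to the MRI portion on day 1, 2 or 3 of the protocol".
- Section 16: assessments are given electronically.

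**The concern.** The urgent part of the pathway starts only when someone reads item 9. PI notification is immediate from that moment, but the moment itself may come up to 24 hours later. A participant can report suicidal ideation, finish the visit and leave while nobody on the team knows. The first response is then a phone call, which depends on reaching the person at a time when they can talk privately. Section 9.2 gives no step for an unanswered call.

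Such a participant could be enrolled as far as the visible criteria show. Section 4.2 excludes psychosis and mania but does not list depression or suicidal ideation. The phone screen is in an appendix that is not visible and may ask about this.

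The means for an in-person response are already described: private testing rooms in Section 9.3 and a nearby emergency facility in Section 18.

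**Working it through.** The question is whether item 9 could be read while the participant is still on site, and how long it may go unread otherwise.

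**Reproducing the plan's total.** The Table 1 maximum times in minutes are:

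- Items 1–14, through the BDI: 30 + 10 + 5 + 5 + 5 + 45 + 10 + 5 + 5 + 5 + 5 + 5 + 5 + 5 = 145.
- Items 15–18: PTSD checklist 5 + substance and alcohol 10 + Bandit practice 5 + Apples practice 5 = 25.
- Total: 145 + 25 = 170, as stated.

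**Time left after the BDI, from listed times.** Remaining time = later items + day-1 scan (60–120 minutes, Section 6.1).

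- Bandit practice on day 1: 25 + 60 = 85 to 25 + 120 = 145 minutes.
- Bandit practice on another day: 20 + 60 = 80 to 20 + 120 = 140 minutes.
- Combined range: 80–145 minutes.

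As a check on scan length, the content listed in Section 12 is 50 (task runs) + 5 (T1) + 12 (diffusion) + 11 (rest) = 78 minutes. This lies inside 60–120 and gives 20 + 78 = 98 to 25 + 78 = 103 minutes. The item times are maxima, so 80 is not a hard floor. With no time for the later items, the scan alone leaves 60 minutes.

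**Time left after the BDI, from the stated session length.** Remaining time = session total − 145.

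- Section 6.1, 3–4 hours on day 1: 180 − 145 = 35 to 240 − 145 = 95 minutes.
- Section 12, 3–6 hours per session: 180 − 145 = 35 to 360 − 145 = 215 minutes.

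**The conflict.** At maximum item times, session 1 would last 170 + 60 = 230 minutes (3.8 h) to 170 + 120 = 290 minutes (4.8 h). That does not fit within 3–4 hours at the upper end, though it fits within 3–6 hours. The documents do not settle which figure is right. Every variant leaves at least 35 minutes.

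**Longest permitted unread time after departure.** This assumes that the clock starts when the BDI is completed and that the whole limit is used.

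- Listed times: 1440 − 145 = 1295 minutes (21.6 h) to 1440 − 80 = 1360 minutes (22.7 h).
- Day-1 total: 1440 − 95 = 1345 minutes (22.4 h) to 1440 − 35 = 1405 minutes (23.4 h).

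These figures are what the rule allows at most. They do not predict actual practice.

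**The case against.** The strongest reply is that Section 9.2 already contains a real pathway: a deadline, a scored trigger, immediate PI notice, senior contact, psychiatric consultation, referral resources and an emergency step. Section 14 adds a DSMB. The 24 hours is an upper limit, and staff may read item 9 during the visit today. All of that is correct. A reader might infer that the protocol has no suicide-risk procedure, or that it obliges staff to wait. The text supports neither. What stands is that the limit sets the minimum protection, and that minimum includes departure unread. The DSMB's annual review and its adverse-event reporting do not bear on when item 9 is read.

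A second reply concerns the timing. No passage gives the on-site time after the BDI, and none says that every questionnaire precedes the scan; only the task practice is placed before it. A fixed scanner slot could change the order. This stands. A reader might infer that 80–145 minutes normally remain, but the Section 6.1 day-1 total gives a lower range, so that inference is not secure. The conclusion needs only enough time to read one answer.

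A third reply is feasibility. Section 16 describes electronic administration but also provides for non-computer forms, and no passage says the platform can flag a single item or that staff are free during the scan. This also stands, and it is why a brief manual check is offered as an alternative to a flag.

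Finally, the participants are healthy controls and no endorsement rate is given. A reader might take a delay of about 22 hours as the expected course, or assume that some of the 42 participants will be affected. The documents support neither.

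**Conclusion.** The point holds as a weakness in a stated rule. Section 9.2 lets a participant who scores 2 or 3 on item 9 leave session 1 before the answer is read, and no other visible section closes that gap. Under either reading of the session length there is time on site to read one item: about 80–145 minutes from listed times, or 35–95 minutes from the day-1 total.

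This rests on three assumptions: the BDI is completed on site in session 1, Table 1 order is followed, and the day-1 scan comes after the questionnaires. The first is inferred from Section 6.1 and Table 1. The other two are inferred from Table 1 and the placing of Apples practice before the scan. The appendices and consent pages are not visible and could add detail.

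The worst case is that item 9 stays unread for most of a day after departure. The number of participants affected cannot be estimated. This is a cheap improvement of low-to-moderate priority. It has no bearing on the endpoints, sample size or analysis.

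**What to change.** In Section 9.2, replace the 24-hour limit with a requirement that item 9 be reviewed before the participant leaves session 1, by a flag on the electronic form or a brief staff check. If the score is 2 or 3, notify the PI at once. When a senior team member is available, carry out the existing steps in person in a private room, in consultation with the attending psychiatrists as now. Keep the phone call as the fallback.

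The cost is a short text change, a brief check per participant (42 in all), and a senior team member reachable on session-1 days. If none is reachable, a flagged participant may still go home and be phoned. The gain is then limited to earlier reading and earlier PI notification.
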